3.3.3 Exclusion criteria

- Patients with asthma as concurrent baseline condition at the time of screening
- Patients with confirmed, suspected or recovered SARS-CoV-2 infection or if the patient had household or other contact with an individual with confirmed SARS-CoV-2 infection within 14 days prior to the completion of the eligibility questionnaire.

16 Sep 2021

Page 30 of 93

Proprietary confidential information © 2021 Boehringer Ingelheim International GmbH or one or more of its affiliated companies

- Patients with a worsening COPD episode requiring medical intervention within 4 weeks of enrolment
- Patients who have completed a pulmonary rehabilitation (PR) or COPD self-management program in the 3 months prior to enrolment or patients who are currently in a PR program (rationale: PR programs typically include a self-management component which may interfere with study objectives)
- Planned vacation or other travel during the study period that requires overnight stays away from home
- Major surgery performed within 6 weeks prior to enrolment or planned during the course of the study, e.g. hip replacement
- Patients prescribed inhaled COPD medications other than Spiriva Respimat plus albuterol or Stiolto Respimat plus albuterol
- Patients with any contraindications for participating in the study (after discussion with their physician).
- Previous enrolment in a TARA study
- Previous enrolment in this study
- Currently enrolled in another investigational device or drug study/trial, or less than 30 days since ending another investigational device or drug trial(s), or receiving other investigational treatment(s)
- Women who are pregnant, nursing, or who plan to become pregnant while in the study
- Any self-reported medical or neuro-cognitive condition that would limit the ability of the participant to consent
- Residence in State of California (rationale: new data management and privacy laws in this state present complications to an effective data analysis plan by allowing users to potentially withdraw their data from the study)

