3.3.4.2 Discontinuation of participants

Participants will be discontinued from the study if they experience an infection with SARS-CoV-2.

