4.2.2 Restrictions

4.2.2.1 Restrictions regarding concomitant treatment

For a participant to be eligible for the study, they must be prescribed Spiriva plus albuterol or Stiolto plus albuterol according to the approved prescribing information. Participants that are additionally prescribed other inhaled COPD medications are not eligible.

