#### 7.2 CONCOMITANT DISEASES AND MEDICATION

Not applicable due to limited data collected.

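### The exclusion for competing programmes leaves out ongoing self-management programmes other than PR, and any programme planned for the study period, contrary to its own rationale

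*Protocol*

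**What the plan says.** Protocol Section 3.3.3 has two limbs. The first covers both kinds of programme, but only once finished: "Patients who have completed a pulmonary rehabilitation (PR) or COPD self-management program in the 3 months prior to enrolment". The second covers current attendance and names PR alone; where the two limbs meet, the text reads "self-management program in the 3 months prior to enrolment or patients who are currently in a PR program". The synopsis has the same two limbs. Section 3.3.3 gives the reason: "PR programs typically include a self-management component which may interfere with study objectives".

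Other items in that list look ahead. Surgery is covered as "Major surgery performed within 6 weeks prior to enrolment or planned during the course of the study", and the travel and pregnancy criteria also refer to plans for the study period. The PR and self-management criterion has no such wording.

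The later rules that can be seen do not address the matter. Section 3.3.4.2 gives one ground for discontinuing a participant: "Participants will be discontinued from the study if they experience an infection with SARS-CoV-2". Section 4.2.2.1 concerns inhaled medication at entry: "Participants that are additionally prescribed other inhaled COPD medications are not eligible". Section 4.2.2.2 places no restriction on diet or lifestyle. The important protocol deviations in SAP Section 6.2 concern entry criteria and consent only.

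The primary assessments are the change in CRQ-SAI dyspnea from baseline to week 12 and whether it reaches 0.5 (Protocol Section 7.2.2, SAP Section 7.4). Each participant is compared with their own baseline, and there is no control group (Protocol Sections 3.1 and 3.2).

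**The concern.** The sponsor identified competing self-management training as a threat and wrote a criterion against it. The criterion stops short of the exposure named in its own reason. A site applying it literally turns away someone who finished a self-management course 11 weeks ago, admits someone attending one now, and admits someone booked to start PR in week 2 of the intervention.

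TARA teaches self-management of breathlessness. PR or another self-management programme can act on the same score over the same 12 weeks. Without a control group, the week-12 change does not separate the two sources. The preliminary analysis in Protocol Section 7.2.1 asks only whether breathlessness fell because activity fell. A programme that maintains or raises activity would pass that check.

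**Working it through.** **Coverage of the criterion.** Setting programme type against timing, with enrolment meaning signed consent (Protocol Section 3.3):

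| Timing | PR | COPD self-management programme other than PR |
|---|---|---|
| Completed within 3 months before enrolment | excluded | excluded |
| Ongoing at enrolment | excluded | not covered |
| Planned for the study period | not covered | not covered |

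Three of the six cells are open. None of the later rules set out above closes them.

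**Which open cell matters most.** Baseline is Survey 1, completed after the 2-week run-in (Protocol Section 6.2.1, SAP Section 6.7). Any gain made before Survey 1 is in the baseline score and cancels in the difference. For a programme already under way, only further gain after Survey 1 counts. For a programme started after Survey 1, all of its gain counts. The bottom row is therefore the stronger route.

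**Size at the planned cohort.** The documents contain no figure to reproduce: 25 per cohort rests on a literature review and expert consultation (Protocol Section 7.5). Inputs are n = 25 and the threshold of 0.5. Assumptions are k affected participants and a gain d of 0.5 to 1.5 points per affected participant from the other programme. All 25 are taken to have both surveys.

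- Responder percentage, upper limit: 100 × k / n. For k = 1, 100 × 1/25 = 4 points. For k = 3, 12 points. For k = 5, 20 points.
- Mean change: k × d / n. For k = 1, 0.5/25 = 0.02 to 1.5/25 = 0.06. For k = 3, 0.06 to 0.18. For k = 5, 0.10 to 0.30.
- Number needed for a cohort mean of 0.5 if TARA and everything else contribute nothing: k = 0.5 × 25 / d, rounded up. This gives 25, 13 and 9 of 25 for d = 0.5, 1.0 and 1.5.

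The 4 points require that the participant would otherwise have been a non-responder. If instead the other programme raises the chance of response from 30% to 70% (assumed), the expected percentage with k = 1 is (24 × 0.30 + 1 × 0.70)/25 = 31.6%, a rise of 1.6 points over 30%. With k = 3 it is (22 × 0.30 + 3 × 0.70)/25 = 34.8%, a rise of 4.8 points.

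**The case against.** The strongest defence is that the protocol already accepts this kind of uncertainty. Section 3.2 says that Phase IIa decides only whether a treatment deserves stricter testing, and leaves the source of an effect to Phase IIb. That stands as to what the study can claim. It does not explain a half-built guard: the sponsor chose to exclude this exposure, and completing the exclusion needs no control group.

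A second defence is that such patients might be kept out anyway, by the physician-judged contraindication criterion or by the aim of enrolling more people who are not yet acting on their COPD (Section 3.3). Either might help, but neither requires it.

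Several stronger readings are tempting and are not supported:

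- A reader might infer that a current attender always confounds more than a recent completer, or that the bias always favours TARA. Gain before Survey 1 cancels, and if a programme ends mid-study and its benefit fades, the bias runs against TARA.
- A reader might infer that the data could not reveal the exposure. Survey 5 includes healthcare resource utilization (Protocol Section 10.1.1), whose items are not visible and may capture PR. The line in SAP Section 7.2, "Not applicable due to limited data collected", is about diseases and medication, so it does not show that programme attendance went unrecorded.
- A reader might rescale the arithmetic to the 5 participants in SAP Section 4. That section replaces the planned analyses with listings, so there is no responder percentage or mean to shift.

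**Conclusion.** The criterion is inconsistent with its own rationale, in Section 3.3.3 and in the synopsis. This follows from the wording and needs no assumption. The consequence is conditional: if a participant was in, or started, an uncovered programme, any resulting change after Survey 1 is counted with TARA's.

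At 25 per cohort the effect is modest. One participant adds at most 4 percentage points to the responder percentage and 0.02 to 0.06 to the mean, which is 4% to 12% of the 0.5 threshold (0.02/0.5 and 0.06/0.5). Several affected participants could visibly move the responder percentage. Such programmes alone are unlikely to produce a mean change of 0.5, since that would take 9 to 25 of 25 participants under the assumed gains.

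A reader might go further and infer that improvement was in fact wrongly credited to TARA. The documents do not support that, because they do not show that anyone in such a programme enrolled. With 5 participants and listings only, the practical issue is how to read each individual Yes or No.

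**What to change.** 1. Reword the criterion in Section 3.3.3 and the synopsis so that PR and COPD self-management programmes are treated alike, whether completed within 3 months before enrolment, ongoing at enrolment, or planned for the study period.
2. Confirm that the Survey 5 healthcare resource utilization items ask whether the participant started such a programme after Survey 1. If they do not, add one item.
3. List that status beside each participant's CRQ-SAI dyspnea change. SAP Section 4 currently limits the further assessments listed to TARA engagement, so this needs a line there. If responder percentages are calculated, show them with and without the participants concerned. Nobody is removed from the main result.
4. With recruitment ended at 5, rewording cannot change who entered. List whatever programme information was collected, or state the limitation in the abbreviated report, and correct the criterion before it is reused in a later study.

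The cost is one sentence in the criteria, at most one survey item and one listing column. In a study still recruiting, a few candidates would be lost.

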3.3.4 Withdrawal of participants from study participation

3.3.4.1 Withdrawal of consent to study participation

Participants may withdraw consent to study participation at any time without the need to justify the decision.

3.3.4.2 Discontinuation of participants

Participants will be discontinued from the study if they experience an infection with SARS-CoV-2.

3.3.4.3 Discontinuation of the study by the sponsor

Boehringer Ingelheim reserves the right to discontinue the study at any time for the following reasons:

- 1. Failure to meet expected enrolment goals.
- 2. Emergence of any new information invalidating the positive benefit-risk assessment that could significantly affect the continuation of the study.

352 2154

Page 31 of 93

16 Sep 2021

Proprietary confidential information © 2021 Boehringer Ingelheim International GmbH or one or more of its affiliated companies

4. TREATMENTS

4.1 INVESTIGATIONAL INTERVENTION

No IMP treatments will be administered in this study.

4.2 OTHER TREATMENTS, EMERGENCY PROCEDURES, RESTRICTIONS

4.2.1 Other treatments and emergency procedures

There are no special emergency procedures to be followed.

There are no restrictions regarding medications for other (non-COPD) diseases.

4.2.2 Restrictions

4.2.2.1 Restrictions regarding concomitant treatment

For a participant to be eligible for the study, they must be prescribed Spiriva plus albuterol or Stiolto plus albuterol according to the approved prescribing information. Participants that are additionally prescribed other inhaled COPD medications are not eligible.

4.2.2.2 Restrictions on diet and lifestyle

There are no restrictions regarding diet and lifestyle.

Clinical Study Protocol Outline

16 Sep 2021

Page 32 of 93

Proprietary confidential information © 2021 Boehringer Ingelheim International GmbH or one or more of its affiliated companies

5. FURTHER DETAILS REGARDING ASSESSMENTS

5.1 ASSESSMENT OF EFFICACY

5.1.1 Primary Assessment

Chronic Respiratory Questionnaire – Self Administered Individualized (CRQ-SAI)

The CRQ-SAI, a derivate of the original CRQ tool, is used to assess the patients' perception of their COPD and measures the impact of COPD on their life. The CRQ-SAI has 20 items over 4 domains: dyspnea, fatigue, emotional function and mastery. For dyspnea, participants are asked to select 5 activities associated with breathlessness (from a list of 26 or custom response), that they have performed in the past two weeks and that are most important to them and indicate how much breathlessness they have experienced while performing each.

The CRQ-SAI should be completed by the participants at the time points outlined in the flow chart. Details of the CRQ-SAI are provided in Appendix 10.2.1.

5.1.2 Secondary Assessments

Activity Tracker (device)

A physical activity tracker is an accelerometer that is used to measure the overall movement of a patient. Activity trackers provide valuable information on physical activity directly from the patient's body.

The device will be the activity tracker used in the study to measure the amount (steps) and intensity (cadence) of daily ambulatory activities in support of the main research objective. Participants will wear the activity tracker throughout the study and the data obtained from the activity tracker will be transferred to the study database.

Instructions will be given to the participants on how to use the activity tracker.

Clinical Visit PROactive Physical Activity in COPD instrument (C-PPAC)

A secondary measure of efficacy is the C-PPAC, a hybrid measurement tool incorporating a patient-reported outcome (PRO) and an activity tracker. The tool couples the difficulties associated with performing physical activity and the amount and intensity of the activities and the final instrument incorporates both a difficulty domain consisting of 10 questions and an amount domain consisting of 4 questions and 2 of these questions are based on data from the activity tracker.

The difficulty domain includes questions related to breathlessness, but also includes questions related to other aspects of the difficulty associated with performing daily activities in IwCOPD.

The C-PPAC should be completed by the participants at the time points outlined in the flow chart. Details of the C-PPAC are provided in Appendix 10.2.2.

16 Sep 2021

Clinical Study Protocol Outline Page 33 of 93

Proprietary confidential information © 2021 Boehringer Ingelheim International GmbH or one or more of its affiliated companies

16 Sep 2021

Clinical Study Protocol Outline Page 34 of 93

Proprietary confidential information © 2021 Boehringer Ingelheim International GmbH or one or more of its affiliated companies

16 Sep 2021

Clinical Study Protocol Outline Page 35 of 93

Proprietary confidential information © 2021 Boehringer Ingelheim International GmbH or one or more of its affiliated companies

16 Sep 2021

Clinical Study Protocol Outline Page 36 of 93

Proprietary confidential information © 2021 Boehringer Ingelheim International GmbH or one or more of its affiliated companies

Page 37 of 93

16 Sep 2021

5.2 ASSESSMENT OF ENGAGEMENT AND PERCEPTIONS OF VALUE

Relevant information regarding assessment of engagement and perceptions of value is provided in Section 2.3 (Further research questions and further assessments) and in the 352-2154 Interview Guide.

5.3 ASSESSMENT OF SAFETY

5.3.1 Physical examination

NA

5.3.2 Vital signs

NA

5.3.3 Safety laboratory parameters

No safety laboratory parameters will be determined.

5.3.4 Electrocardiogram

NA

5.3.5 Other safety parameters

NA

5.3.6 Assessment of adverse events

5.3.6.1 Definitions of AEs

5.3.6.1.1 Adverse event

Adverse event

An adverse event (AE) is defined as any untoward medical occurrence in a patient or clinical investigation subject administered a medicinal product and which does not necessarily have a causal relationship with this treatment. An adverse event can therefore be any unfavourable and unintended sign (e.g. an abnormal laboratory finding), symptom, or disease temporally associated with the use of a medicinal product, whether or not considered related to the medicinal product.

Adverse drug reaction

16 Sep 2021

Page 38 of 93

Proprietary confidential information © 2021 Boehringer Ingelheim International GmbH or one or more of its affiliated companies

An adverse drug reaction (ADR) is defined as a response to a medicinal product which is noxious and unintended. Response in this context means that a causal relationship between a medicinal product and an adverse event is at least a reasonable possibility. Adverse reactions may arise from use of the product within or outside the terms of the marketing authorisation or from occupational exposure. Conditions of use outside the marketing authorization include off-label use, overdose, misuse, abuse and medication errors.

Serious adverse event

A serious adverse event is defined as any AE which

- results in death,
- is life-threatening,
- requires in-patient hospitalization, or
- prolongation of existing hospitalization,
- results in persistent or significant disability or incapacity, or
- is a congenital anomaly/birth defect

Life-threatening in this context refers to a reaction in which the patient was at risk of death at the time of the reaction; it does not refer to a reaction that hypothetically might have caused death if more severe.

Medical and scientific judgement should be exercised in deciding whether other situations should be considered serious reactions, such as important medical events that might not be immediately life threatening or result in death or hospitalization but might jeopardize the patient or might require intervention to prevent one of the other outcomes listed above. Examples of such events are intensive treatment in an emergency room or at home for allergic bronchospasm, blood dyscrasias or convulsions that do not result in hospitalization or development of dependency or abuse. Any suspected transmission via a medicinal product of an infectious agent is also considered a serious adverse reaction.

Adverse Event of Special Interest (AESI)

The term Adverse Event of Special Interest (AESI) relates to any specific AE that has been identified at the project level as being of particular concern for prospective safety monitoring and safety assessment within this study, e.g. the potential for AEs based on knowledge from other compounds in the same class.

No AESIs have been defined for this study.

5.3.7 Adverse Event Collection and Reporting

The investigator shall maintain and keep detailed records of all AEs in their patient files.

5.3.7.1 Collection of AEs

The investigator carefully assesses whether an AE constitutes an ADR using the information below.

16 Sep 2021

Page 39 of 93

Proprietary confidential information © 2021 Boehringer Ingelheim International GmbH or one or more of its affiliated companies

Causal relationship of adverse event

The definition of an adverse reaction implies at least a reasonable possibility of a causal relationship between a suspected medicinal product and an adverse event. An adverse reaction, in contrast to an adverse event, is characterized by the fact that a causal relationship between a medicinal product and an occurrence is suspected.

Medical judgment should be used to determine the relationship, considering all relevant factors, including pattern of reaction, temporal relationship, de-challenge or re-challenge, confounding factors such as concomitant medication, concomitant diseases and relevant history.

Arguments that may suggest a reasonable causal relationship could be:

- The event is **consistent with the known pharmacology** of the drug
- The event is known to be caused by or attributed to the drug class
- A plausible time to onset of the event relative to the time of drug exposure
- Evidence that the **event is reproducible** when the drug is re-introduced
- **No medically sound alternative etiologies** that could explain the event (e.g. pre-existing or concomitant diseases, or co-medications).
- The event is typically **drug-related and infrequent in the general population** not exposed to drugs (e.g. Stevens-Johnson syndrome).
- An indication of dose-response (i.e. greater effect size if the dose is increased, smaller effect size if dose is diminished).

Arguments that may suggest that there is **no reasonable possibility of a causal relationship** could be:

- No plausible time to onset of the event relative to the time of drug exposure is evident (e.g. pre-treatment cases, diagnosis of cancer or chronic disease within days/weeks of drug administration; an allergic reaction weeks after discontinuation of the drug concerned)
- Continuation of the event despite the withdrawal of the medication, taking into
 account the pharmacological properties of the compound (e.g. after 5 half-lives).
 Of note, this criterion may not be applicable to events whose time course is prolonged
 despite removing the original trigger.
- Additional arguments amongst those stated before, like alternative explanation (e.g. situations where other drugs or underlying diseases appear to provide a more likely explanation for the observed event than the drug concerned).
- Disappearance of the event even though the study drug treatment continues or remains unchanged.

Intensity of adverse event

The intensity of the AE should be judged based on the following:

Mild: Awareness of sign(s) or symptom(s) which is/are easily tolerated Moderate: Enough discomfort to cause interference with usual activity

Severe: Incapacitating or causing inability to work or to perform usual activities

16 Sep 2021

Page 40 of 93

Proprietary confidential information © 2021 Boehringer Ingelheim International GmbH or one or more of its affiliated companies

Pregnancy:

In rare cases, pregnancy might occur in a study. Once a patient has been enrolled in the study and has taken study Spiriva Respimat or Stiolto Respimat, the investigator must report any drug exposure during pregnancy in a study participant within 7 days by means of Part A of the Pregnancy Monitoring Form to the sponsor's unique entry point. See table below.

Similarly, potential drug exposure during pregnancy must be reported if a partner of a male trial participant becomes pregnant. This requires a written consent of the pregnant partner. The ISF will contain the trial specific information and consent for the pregnant partner.

The outcome of the pregnancy associated with the drug exposure during pregnancy must be followed up and reported to the sponsor's unique entry point on the Pregnancy Monitoring Form (Part B).

The ISF will contain the Pregnancy Monitoring Form (Part A and B). As pregnancy itself is not to be reported as an AE, in the absence of an accompanying serious ADR, only the Pregnancy Monitoring Form and not the AE form is to be completed. If there is a serious ADR associated with the pregnancy a AE form must be completed in addition.

The study design is of non-interventional nature and the study is conducted within the conditions of the approved marketing authorization. Sufficient data from controlled interventional trials are available to support the evidence on the safety and efficacy of the studied BI drug.

The following AE collection and reporting requirements have been defined:

All AEs and other safety relevant information identified via all sources used in the study have to be reported [via the study website (i.e. questionnaires), interviews, TARA platform] to the investigator for causality assessment (Section 5.3.7) and reporting to sponsor regardless of causal relationship.

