1.4.1 Benefits

Potential benefits of the fully developed TARA DBCI include improving knowledge of COPD and its treatments and how treatment can improve symptoms and outcomes, verifying inhaler technique, and learning new skills that may improve self-management of COPD; these same potential benefits are applicable to study participants engaging with the TARA DBCI working prototype (version 3).

1.4.2 **Risks**

No adverse effects have been identified during the user experience testing rounds of components of the intervention or in the first clinical study (CRT1; 352.2133).

Study 352.2154 will be the second study that IwCOPD will engage with TARA in a real-world setting. There is a potential for (disease-related) behaviour change and consequent risks associated with changes in behaviour; in light of the fact that (i) study participants will only be allowed to log-on to TARA after recommendation by their primary physician, (ii) the

16 Sep 2021

Page 20 of 93

Proprietary confidential information © 2021 Boehringer Ingelheim International GmbH or one or more of its affiliated companies

medical oversight of the participant is by their primary physician and (iii) no therapeutic recommendations are being provided by the software, risks associated with engagement with TARA in this study are considered low. The time required to engage with TARA is a potential inconvenience and is mitigated by the option for study participants to disengage from TARA / study at any time.

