11. DESCRIPTION OF GLOBAL AMENDMENT(S)

11.1 AMENDMENT 1

Date of amendment	16 Sep 2021	
EudraCT number	NA	
EU number		
BI Trial number	352-2154	
BI Investigational Medicinal	TARA DBCI prototype (version 3)	
Product(s)		
Title of protocol	Proof of concept (proof of intervention	
	principles) study assessing effects of Technology-	
	Assisted Respiratory Adherence prototype	
	version 3 (a Digital Behaviour Change	
	Intervention, DBCI) on proximal clinical	
	outcomes and mediators (psychological	
	mediators, self-management behaviours) in	
	individuals with COPD (IwCOPD)	
Global Amendment due to urgent sa	afety reasons	
Global Amendment		X
	L my d	
Section to be changed	Title page	
Description of change	Allocation of new CTL	
Rationale for change	Change in CTL	
Section to be changed	Sections 2.3, 5.1.3.1, 10.1.1, 10.2.5.	
Description of change		
Section to be changed	Synopsis, Section 3.3.3	"
Description of change	Exclusion criterion 1 – updated from	
	with asthma" to "Patients with asthma as	
	concurrent baseline condition at the time of	
	screening"	
Rationale for change	Clarification to all enrolment of patients with a	
	historical diagnosis of asthma	
Section to be changed	Synopsis, Section 3.3.3	
Description of change	Exclusion criterion 2 - updated to include a	
	timeframe for contacts with an infected person	
	prior to the completion of the eligibility	
	questionnaire.	

16 Sep 2021

Page 92 of 93

Rationale for change	Updated to allow the enrolment of patients who have been in contact with persons infected with SARS COV-19, but are not infected themselves	
Section to be changed	Section 5.3.7	
Description of change	All AEs and SAEs are to be reported to BI GPV regardless of causal relationship to Spiriva Respimat or Stiolto Respimat	
Rationale for change	Clarification of AE reporting requirements to ensure all identified events will be evaluated and reported accordingly.	
Section to be changed	Synopsis, Sections 3.1, 7.2.7	
Description of change	Removal of interim analysis	
Rationale for change	Based on the observed TARA use by the first enrolled patients of cohort 1, an interim analysis between cohort 1 and cohort 2 is no longer expected to provide meaningful results.	
Section to be changed	Section 7.2.1	
Description of change	Clarification that cohorts 1 and 2 will be analysed separately and definition of analysis data set	
Rationale for change	Further clarification on planned data analysis	
Section to be changed	Section 7.2.5.	

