#### 7.8.1 Adverse Events

Unless otherwise specified, the analyses of AEs will be descriptive in nature. All analyses of AEs will be based on the number of subjects with AEs and NOT on the number of AEs.

The analysis of AEs will be based on the concept of treatment emergent AEs. That means that all AEs that occurred after signing the informed consent until the end of study (Week 12) will be assigned to the treatment observed at baseline (background treatment). Non-treatment-emergent AEs will be assigned to "screening" or "follow-up" (after Week 12).

According to ICH E3 (4), in addition to Deaths and serious adverse events, 'other significant' AEs need to be listed in the clinical study report. These will be any non-serious adverse event that led to an action taken with study drug (e.g. discontinuation or dose reduced or interrupted). An overall summary of adverse events will be presented.

The frequency of subjects with AEs will be summarized by treatment, primary system organ class and PT. Separate tables will be provided for subjects with serious adverse events (SAEs), AEs leading to treatment discontinuation, AEs of at least moderate severity and related AEs.

The system organ classes (SOCs) will be sorted by default alphabetically, PTs will be sorted by frequency (within SOC).

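### Relatedness of adverse events is defined only against a medicinal product, so the related-AE table cannot show events attributed to TARA, the product under test

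*Protocol*

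**What the plan says.** **Product under test.** The protocol synopsis lists TARA version 3 as the test product. Protocol 4.1 adds: "No IMP treatments will be administered in this study". SAP 6.1 likewise says that the study neither assigns nor administers a pharmacological treatment.

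**Definitions.** Protocol 5.3.6.1.1 defines an adverse event as "any untoward medical occurrence in a patient or clinical investigation subject administered a medicinal product". An adverse drug reaction is one where "a causal relationship between a medicinal product and an adverse event is at least a reasonable possibility".

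**The investigator's task.** Protocol 5.3.7.1 states: "The investigator carefully assesses whether an AE constitutes an ADR using the information below". It repeats that a reaction implies at least "a reasonable possibility of a causal relationship between a suspected medicinal product and an adverse event".

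**Collection and reporting.** Protocol 5.3.7.1 sends every AE from every source, including questionnaires, interviews and the TARA platform, to the investigator for causality assessment and then to the sponsor. Protocol 5.3.7.2 requires reporting of all AEs and SAEs whatever the cause.

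**Recognised risk.** On engagement with TARA, protocol 1.4.2 says: "There is a potential for (disease-related) behaviour change and consequent risks associated with changes in behaviour". It rates the risk as low and reports no adverse effects in user testing or in the first clinical study.

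**Output.** Protocol 7.2.5 tabulates causal relationship. SAP 7.8.1 assigns AEs to the background treatment seen at baseline and plans separate tables that include "AEs of at least moderate severity and related AEs".

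**The concern.** Causality is asked about the inhalers, which are marketed background therapy, and not about the product that the study exists to evaluate. The protocol names one kind of harm specific to TARA, namely risk that follows from a change in behaviour, but no step in the safety plan asks whether an event arose that way.

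The consequence lies in how the result is read. Protocol 1.3 says that the study will help decide whether TARA merits a larger randomised trial, and 1.4.2 already relies on the absence of adverse effects in the previous study. A related-AE table from this study would naturally be cited in the same way. If it is empty, it tells the reader about two inhalers and nothing about TARA, and neither document warns the reader of that.

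**Working it through.** No arithmetic applies, because the plan states no figure on this point. The check is to follow one event from collection to the final table.

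1. **Is it collected?** Yes. The AE definition refers to a medicinal product, but eligibility requires every participant to have a prescription for one of the two inhalers, and 5.3.7.1 and 5.3.7.2 cover all AEs from consent onwards. Collection does not depend on cause.

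2. **What is the investigator asked?** Only whether the event is an adverse drug reaction. Protocol 5.3.7.1 also sends AEs found through TARA to causality assessment under 5.3.7, that is, to the same drug-based criteria.

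3. **What criteria apply?** Protocol 5.3.7.1 lists seven arguments for a causal link and four against. Of these eleven, nine name the drug or medication (pharmacology, class, exposure time, re-introduction, withdrawal and so on), one concerns dose-response, and one (no other sound explanation) names no product. None mentions TARA, software, behaviour change or the tracker. One argument against relatedness is that something other than the drug explains the event better.

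4. **Could medicinal product be meant to include TARA?** The amendment header does enter TARA in a template field for the investigational medicinal product. Three things go against that reading: protocol 4.1 says no IMP is given; the criteria in step 3 do not fit software; and the amendment's entry on AE reporting names Spiriva Respimat and Stiolto Respimat as the products to which causality refers.

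5. **What reaches the report?** SAP section 4 replaces the planned analyses with listings because 5 participants were recruited instead of 50. SAP 7.8 nevertheless keeps the safety analysis as the protocol defines it, and 7.8.1 keeps the related-AE table. AEs are summarised by background treatment, and other significant AEs are defined by action taken with a study drug. The split by cohort in SAP 6.1 shows which TARA version a participant used, but that is not a causality judgement.

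Two hypothetical events show the result:

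| Event | Judgement under 5.3.7.1 | Place in the SAP tables |
|---|---|---|
| Harm while practising a breathing or pacing technique taught by TARA, with no link to the inhaler | Not a drug reaction | All AEs only |
| Harm from inhaler misuse or a medication error prompted by the Cohort 2 medication support | Can be a drug reaction, since 5.3.6.1.1 includes misuse, overdose and medication errors | Related AEs, credited to the drug |

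Both events are reported, and neither can be labelled as related to TARA.

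**The case against.** The strongest reply is that nothing is lost. All AEs go to the investigator and the sponsor with set timelines and follow-up, the site asks about AEs at the follow-up visit (6.2.3), and interviewers monitor for them (10.3). With 5 participants, someone can read each event individually, no inference rests on the related count, and no adverse effect of TARA has been seen so far. The AE form and the Investigator's Brochure are not among the documents, so the form may already have a TARA field.

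Much of this stands. A reader might infer that harm from TARA would go undetected or unreported; the reporting rules in 5.3.7.1 and 5.3.7.2 rule that out. A reader might also infer that every TARA-caused event would be classed as unrelated. That does not follow either, because harm through misuse of the inhaler could be classed as a drug reaction. As the form cannot be seen, the supportable statement is that the plan does not call for a TARA judgement, not that none was made.

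What the reply does not remove is the label. A small number of events makes the repair easy, but it does not make a table headed as related AEs speak to TARA. Even if the form has such a field, the SAP has no output for it. The case for including the activity tracker is weaker, since 1.4.2 names no tracker risk; that part is optional.

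**Conclusion.** The point holds as a gap in attribution. Under the plan as written, the number of AEs that can be labelled TARA-related is zero by definition, whatever happens to participants, and the related-AE table cannot be used as evidence on the safety of TARA. Collection and reporting of events are intact.

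I attach no probability to a TARA-caused event. The documents give no rate, 1.4.2 reports no adverse effects to date, and the gap is the same at any rate. The practical size is modest: a few events at most in 5 participants, in an abbreviated report. It still merits correction, because the study's purpose is to inform a decision on further testing of TARA and the missing judgement concerns the one product-specific risk that the protocol names.

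The conclusion assumes that medicinal product means the inhalers, as the criteria and the amendment indicate, and that no document outside this set adds a TARA causality question.

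**What to change.** - **Protocol 5.3.6.1 and 5.3.7.1:** beside the drug judgement, add a separate investigator judgement for each AE of whether it is related to TARA, with criteria that suit a behavioural intervention. The activity tracker can be added optionally.
- **SAP 7.8.1:** report drug-related and TARA-related AEs separately and state which product each heading refers to.
- **Events already collected:** obtain the TARA judgement before database lock and label it as retrospective.
- **If that is not possible:** state in the report that related means drug-related and that relatedness to TARA was not assessed.

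The cost is one extra field, unless the AE form already has it, and a retrospective judgement on a few events. A retrospective judgement is weaker than one made at the time, which is why it should be labelled. The fallback costs one sentence in the report.
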